7.3. Pharmacokinetic Parameters

Actual PK sampling times will be used in the derivation of PK parameters.

If a PK parameter cannot be derived from a subject's concentration data, the parameter will be coded as NC (ie not calculated). (Note that NC values will not be generated beyond the day that a subject discontinues).

In summary tables, statistics will be calculated by setting NC values to missing; and statistics will be presented for a particular hepatic function group with ≥ 3 evaluable measurements.

For statistical analyses (ie analysis of variance), PK parameters coded as NC will also be set to missing and analyses will not be performed for a particular parameter if more than 50% of the data are NC.

If an individual subject has a known biased estimate of a PK parameter (due for example to an unexpected event such as vomiting before all the compound is adequately absorbed in the body), this will be footnoted in summary tables and will not be included in the calculation of summary statistics or statistical analyses.

8. STATISTICAL METHODOLOGY AND STATISTICAL ANALYSES

8.1. Statistical Methods

The effect of hepatic impairment on PK parameters will be assessed by constructing 90% confidence intervals around the estimated differences between the Test (impaired hepatic function group) and the Reference (normal hepatic function group) PK parameters using a one-way ANOVA model based on natural log transformed data.

8.2. Statistical Analyses

Analysis of variance (ANOVA) will be used to compare the natural log transformed AUC_{inf} (if data permit), AUC_{last} and C_{max} between normal hepatic function group and the impaired hepatic function group. Estimates of the adjusted mean differences (Test-Reference) and corresponding 90% confidence intervals will be obtained from the model. The adjusted

mean differences and 90% confidence intervals for the differences will be exponentiated to provide estimates of the ratio of adjusted geometric means (Test/Reference) and 90% confidence intervals for the ratios. The normal hepatic function group will be the Reference group and the impaired hepatic function group will be Test group.

Residuals from the models will be examined for normality and the presence of outliers via visual inspection of plots of residuals vs predicted values and normal probability plots of residuals, but these will not be included in the clinical study report. If there are major deviations from normality or outliers then the effect of these on the conclusions will be investigated through alternative transformations and/or analyses excluding outliers.

Justification for any alternative to the planned analyses will be provided in the report of the study.

The following PK parameters will be summarized by hepatic function group:

Table 3. PK Parameters to be Summarized Descriptively by Group

Parameter	Summary Statistics
AUC _{last} , AUC _{inf} , C _{max} , CL and V _{ss}	N, arithmetic mean, median, cv%, standard deviation, minimum, maximum, geometric mean and geometric cv%.
T _{max}	N, median, minimum, maximum.
t _{1/2}	N, arithmetic mean, median, cv%, standard deviation, minimum, maximum.

Box and whisker plots for individual subject parameters (AUC_{inf}, AUC_{last} and C_{max}) will be presented by hepatic function group and overlaid with geometric means.

Supporting data from the estimation of t_{1/2} and AUC_{inf} will be listed by hepatic function group: terminal phase rate constant (k_{el}); goodness of fit statistic from the log-linear regression (r²); the percent of AUC_{inf} based on extrapolation (AUC_{extrap%}); and the first, last, and number of time points used in the estimation of k_{el}. This data may be included in the clinical study report.

Presentations for PF-06460031 concentrations will include:

- A listing of all concentrations sorted by hepatic function group (present in heading), subject id and nominal time postdose. The concentration listing will also include the actual times. Deviations from the nominal time will be provided in a separate listing.
- A summary of concentrations by hepatic function group and nominal time postdose, where the set of statistics will include n, mean, median, standard deviation, coefficient of variation (cv), minimum, maximum and the number of concentrations above the lower limit of quantification.

- Median concentrations time plots (on both linear and semi-log scales) against nominal time postdose by hepatic function group (both hepatic function groups on the same plot per scale, based on the summary of concentrations by hepatic function group and time postdose).
- Mean concentrations time plots (on both linear and semi-log scales) against nominal time postdose by hepatic function group (both hepatic function groups on the same plot per scale, based on the summary of concentrations by hepatic function group and time postdose).
- Individual concentration time plots by hepatic function group (on both linear and semi-log scales) against actual time postdose (there will be separate spaghetti plots for each hepatic function group per scale).

For summary statistics and median/mean plots by sampling time, the nominal PK sampling time will be used. For individual subject plots by time, the actual PK sampling time will be used.

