# 2. STUDY OBJECTIVES AND ENDPOINTS

Primary Objectives:	Primary Endpoints:
• To evaluate the effect of moderate hepatic impairment on the PK of rivipansel following single 840 mg IV dose.	• Primary: AUC inf (or AUC last , as data permit), CL.
• To evaluate the safety and tolerability of a single 840 mg IV dose of rivipansel in subject with moderate hepatic impairment and in healthy subjects with normal hepatic function	
 
Safety will be assessed by physical examinations, AE monitoring, 12-lead ECGs, supine blood pressure (BP) and pulse rate, and safety laboratory tests.
 

Secondary Objective(s):	Secondary Endpoint(s):
• To evaluate the effect of moderate hepatic impairment on additional PK parameters for rivipansel following a single 840 mg IV dose.	• Secondary: AUC last , $C_{max}$ , $t_{1/2}$ , $V_{ss}$ .

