6.3. Other Endpoints

6.3.1. PK Endpoints

Blood samples for PK analysis of PF-06460031 will be collected according to the Schedule of Activities given in the protocol.

The following PK parameters will be calculated for PF-06460031 (if possible) from the concentration-time data using standard non-compartmental methods:

Table 2. Noncompartmental PK Parameters

PK Parameter	Analysis Scale	PF-06460031
AUC _{inf} [*]	ln	A, D
AUC _{last}	ln	A, D
C _{max}	ln	A, D
T _{max}	R	D
t _{1/2} [*]	R	D
CL [*]	ln	D
V _{ss} [*]	ln	D

Key: A=analyzed using statistical model, D=displayed with descriptive statistics,
ln=natural-log transformed, R=raw (untransformed), *=if data permits

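### Two of the four secondary PK endpoints, half-life and Vss, have no planned Moderate/Normal effect estimate or 90% confidence interval

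*SAP*

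**What the plan says.** Protocol Section 2 words the secondary objective as an effect: "To evaluate the effect of moderate hepatic impairment on additional PK parameters for rivipansel following a single 840 mg IV dose". Four endpoints serve it: AUClast, Cmax, t1/2 and Vss. The primary PK endpoints are AUCinf (with AUClast as fallback) and CL.

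SAP Section 8.1 states how an effect is measured: "The effect of hepatic impairment on PK parameters will be assessed by constructing 90% confidence intervals". The intervals are for impaired minus normal, from a one-way ANOVA on ln-transformed data. That section names no parameters.

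SAP Section 8.2 then applies the ANOVA to AUCinf (if data permit), AUClast and Cmax. SAP Table 2 matches this through its codes ("A=analyzed using statistical model, D=displayed with descriptive statistics"): those three are A, D, while Tmax, t1/2, CL and Vss are D only. The table puts Vss and CL on the ln scale and t1/2 on the raw scale.

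Table 3, introduced by "The following PK parameters will be summarized by hepatic function group", gives Vss a geometric mean and geometric CV, but gives t1/2 only arithmetic statistics, the median and the range. Protocol Section 9.2 has the same split between ANOVA and descriptive parameters.

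**The concern.** Protocol Section 9.1 calls this an estimation study, and SAP Sections 4.1 and 4.2 set no hypotheses or decision rules. The estimate with its interval is therefore the result. For two endpoints listed under an objective about an effect, the reader gets two group summaries of 8 subjects each and must judge the contrast by eye. The plan gives no reason for treating them differently from AUClast and Cmax.

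These two also carry information that AUC does not. The protocol reports that more than 90% of the dose is excreted in urine and excludes subjects with eGFR below 60, so AUC and CL may move little. Ascites and low albumin count towards the Child-Pugh score, and only severe ascites is excluded. If impairment changed distribution while clearance stayed the same, AUC would not show it, but Vss and t1/2 would. In addition, under Protocol Section 7.2.2 the unbound-fraction sample is assayed only if the groups differ in PK. That trigger is not defined, and a Vss contrast would help to inform it.

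**Working it through.** **1. Which endpoints get a contrast.** From Protocol Section 2, SAP Table 2 and SAP Section 8.2:

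| Parameter | Role | Table 2 code, scale | Planned ratio and 90% CI |
|---|---|---|---|
| AUCinf | primary | A, D; ln | yes, if data permit |
| CL | primary | D; ln | no |
| AUClast | secondary (and primary fallback) | A, D; ln | yes |
| Cmax | secondary | A, D; ln | yes |
| t1/2 | secondary | D; raw | no |
| Vss | secondary | D; ln | no |

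Two of the four secondary endpoints have no contrast.

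**2. CL loses nothing.** Protocol Section 9.2.1 defines CL = Dose/AUCinf, and every subject receives 840 mg. So ln CL = ln 840 − ln AUCinf. The Moderate/Normal CL ratio is the reciprocal of the AUCinf ratio, and its confidence limits are the reciprocals in reverse order. No such identity links t1/2 or Vss to AUC.

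**3. What can be rebuilt from Table 3.**
- *Vss.* N, geometric mean (GM) and geometric CV by group are enough. The group SD on the ln scale is s = sqrt(ln(1 + gCV²)). Pool the two variances to get sp. The ratio is GM(moderate)/GM(normal), with 90% limits obtained by multiplying and dividing by exp[t × sp × sqrt(1/n1 + 1/n2)].
- *t1/2.* N, arithmetic mean and SD give a raw-scale difference and its interval. They do not give the geometric mean ratio used for the other parameters. That ratio would need individual values, for example from t1/2 = ln 2/kel. SAP Section 8.2 plans a kel listing but leaves its inclusion in the study report optional.

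**4. Precision if both were analysed.** There is no planned precision figure to reproduce: 8 per group comes from a guidance recommendation, with no SD or target width. Inputs: n = 8 per group, df = 2 × 8 − 2 = 14, t(0.95, 14) = 1.7613.

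Half-width on the ln scale = 1.7613 × sqrt(2/8) × SD_ln = 0.8807 × SD_ln, with SD_ln = sqrt(ln(1 + CV²)). The factor is exp(half-width).

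| CV | SD_ln | Half-width | Factor | 90% CI if ratio = 1 |
|---|---|---|---|---|
| 17.1% | 0.1695 | 0.1493 | 1.16 | 0.86 to 1.16 |
| 25% | 0.2462 | 0.2168 | 1.24 | 0.81 to 1.24 |
| 30% | 0.2936 | 0.2585 | 1.30 | 0.77 to 1.30 |
| 40% | 0.3853 | 0.3393 | 1.40 | 0.71 to 1.40 |

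All the CVs are assumptions. The 17.1% is borrowed from Cmax in healthy subjects (Protocol Section 1.2: 43.7/256 = 0.171). No between-subject CV is given for t1/2 or Vss.

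**5. An illustration of what AUC would miss.** Protocol Section 1.2 gives a volume of 0.130 to 0.181 L/kg, which is 9.1 to 12.7 L at an assumed 70 kg. If the drug entered an assumed 2 L of extra fluid, the volume would rise by 2/9.1 = 22% to 2/12.7 = 16%. With CL unchanged, AUC stays the same. With t1/2 approximated as ln 2 × V/CL, half-life rises by the same 16% to 22%. This shows what a shift could look like; the documents do not predict one.

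**The case against.** The best defence is that the plan is coherent. Protocol Section 9.2, SAP Table 2, SAP Section 8.2 and Table 3 all treat t1/2, CL and Vss descriptively. Section 8.1 can be read as a general sentence that Section 8.2 narrows. No decision depends on either interval. A Vss ratio can be recovered from the report, and so can a raw-scale t1/2 difference. Cmax after a 20-minute infusion, with a half-life near 7 hours, depends mainly on the initial distribution volume, and it does have a planned interval. An unbound-fraction sample is also available. One sentence in Section 8.1 calling these two parameters descriptive would remove the inconsistency.

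Most of this stands, and it keeps the point minor. It does not remove it. Cmax reflects early volume, not Vss, and would say little about fluid that equilibrates slowly. Rebuilding Vss by hand is no substitute for reporting it. For half-life, the matching ratio cannot be obtained from Table 3.

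A reader might infer three stronger things, none of which the documents support:
- That the secondary objective gets no effect estimate at all. AUClast and Cmax serve it and get a ratio with a 90% interval.
- That the SAP departs from the protocol. The two agree.
- That the primary analysis suffers because CL is also descriptive. Its ratio follows exactly from AUCinf.

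**Conclusion.** The point holds, at minor severity: t1/2 and Vss, half of the secondary PK endpoints, have no planned Moderate/Normal estimate or 90% interval, although the objective and SAP Section 8.1 both speak of an effect. The practical loss is greater for t1/2, whose geometric mean ratio cannot be rebuilt from the planned tables, than for Vss, whose ratio can.

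The factors of 1.16 to 1.40 rest on 8 evaluable subjects per group, roughly log-normal values and assumed CVs of 17% to 40%. They show how precise the missing intervals might be; they do not measure harm. Nor can one say that the precision would equal that for AUC, because the documents give no between-subject CV for AUC, t1/2 or Vss.

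**What to change.** In SAP Table 2, code Vss and t1/2 as A, D, both on the ln scale (t1/2 is now raw). In SAP Section 8.2, add them to the ANOVA list, if data permit and under the existing Section 7.3 rule on parameters that are more than 50% not calculated. Report the Moderate/Normal geometric mean ratio with its 90% interval from the same one-way model. Add the geometric mean and geometric CV for t1/2 to Table 3. CL can be added for completeness. Mirror the list in Protocol Section 9.2 at the next amendment, if there is one.

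The Appendix 1 code already takes the response as a macro variable, so the cost is two more runs and a few table rows. No new samples or subjects are needed, and with no hypotheses there is no error rate to protect. If the sponsor prefers to keep both descriptive, SAP Section 8.1 should say so and give the reason.

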8.3. Safety Analysis

A set of summary tables split by hepatic function group will be produced to evaluate any potential risk associated with the safety and toleration of administering PF-06460031.

8.3.1. Treatment and Disposition of Subjects

Subject evaluation groups will show end of study subject disposition and will show which subjects were analyzed for pharmacokinetics, as well as for safety (adverse events and laboratory data). Frequency counts will be supplied for subject discontinuation(s) by hepatic function group.

Data will be reported in accordance with the sponsor reporting standards.

8.3.2. Demographic and Clinical Examination Data

A break-down of demographic data will be provided for age, race, weight, body mass index, and height. Each will be summarized by sex at birth and 'All Subjects' in accordance with the sponsor reporting standards.

8.3.3. Discontinuation(s)

Subject discontinuations due to adverse events will be detailed and summarized by hepatic function group.

Data will be reported in accordance with the sponsor reporting standards.

8.3.4. Adverse Events

Adverse events will be reported in accordance with the sponsor reporting standards by hepatic function group.

8.3.5. Laboratory Data

Laboratory data will be listed and out of range values will be summarized in accordance with the sponsor reporting standards.

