#### **3. STUDY DESIGN**

## 3.1. Study Overview

This study is a Phase 1 open-label, single-dose, single-treatment, non-randomized study of rivipansel in subjects with moderate hepatic impairment and healthy subjects with normal hepatic function. Since rivipansel is primarily eliminated renally, a reduced study design with two groups (control subjects and subjects with moderate hepatic impairment) was considered adequate to characterize the PK in subjects with hepatic impairment.

The Child-Pugh Score will be utilized to assess entry criteria and to assign subjects to the appropriate hepatic-impairment group. Child-Pugh assessments will be performed within the 14 days prior to study medication administration and Day 0 (baseline). Subjects should satisfy the criteria for Child-Pugh classification as Moderate Hepatic Impairment (Class B Score 7-9) for both assessments in order to be enrolled into the study. The subjects' hepatic function will be ranked based on clinical signs and liver function test results (Table 1).

Assigned Score for Observed Findings		
1 point	2 points	3 points
0	1 or 2	3 or 4
Absent	Slight	Moderate
<2	2 to 3	>3
>3.5	2.8 to 3.5	<2.8
<4	4 to 6	>6
	Assignment           0           Absent           <2	Assigned Score for Observed F1 point2 points01 or 2AbsentSlight<2

Table 1.	Assessment of Her	patic Impairment:	Child-Pugh Score
1	11000000110110 01 110		

cation of clinical severity

Mild (Class A): Total score 5-6 points

Moderate (Class B): Total score 7-9 points

Severe (Class C): Total score >9 points

Grade 0: Normal consciousness, personality, neurological examination, electroencephalogram. a. Grade 1: Restless, sleep disturbed, irritable/agitated, tremor, impaired handwriting, 5 cps (cycles per sec) waves.

Grade 2: Lethargic, time-disoriented, inappropriate, asterixis, ataxia, slow triphasic waves. Grade 3: Somnolent, stuporous, place-disoriented, hyperactive reflexes, rigidity, slow waves. Grade 4: Unrousable coma, no personality/behavior, decerebrate, slow 2-3 cps delta activity. See Appendix 1 for details.

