## 4.2.2. Healthy Subjects with Normal Hepatic Function

- 1. Evidence or history of clinically significant hematological, renal, endocrine, pulmonary, gastrointestinal, cardiovascular, hepatic, psychiatric, neurological, or allergic disease (including drug allergies, but excluding untreated, asymptomatic, seasonal allergies at the time of dosing).
- Screening supine 12-lead ECG demonstrating QTcF (QTc using Fridericia's formula) >450 msec or a QRS interval >120 msec at screening. If QTcF exceeds 450 msec, or QRS exceeds 120 msec, the ECG should be repeated two more times and the average of the three QTcF or QRS values should be used to determine the subject's eligibility.
- Screening supine BP ≥140 mm Hg (systolic) or ≥90 mm Hg (diastolic), on a single measurement following at least 5 minutes of rest. If BP is ≥140 mm Hg (systolic) or ≥90 mm Hg (diastolic), the BP should be repeated two more times and the average of the three BP values should be used to determine the subject's eligibility.
- 4. History of alcohol abuse with a positive alcohol test at screening or on Day 0 at the discretion of the investigator.
- 5. Subjects with ANY of the following abnormalities in safety laboratory tests at screening, as assessed by the study-specific laboratory and confirmed by a single repeat test, if deemed necessary:
  - Aspartate aminotransferase (AST) or alanine aminotransferase (ALT) level > upper limit of normal (ULN);
  - Total bilirubin level > ULN.
- 6. Use of prescription drugs, vitamins, or dietary supplements within 7 days or 5 half-lives (whichever is longer) prior to administration of study medication. As an exception, acetaminophen may be used at doses of ≤1 g/day. Limited use of nonprescription medications that are not believed to affect subject safety or the overall results of the study may be permitted on a case-by-case basis following approval by the sponsor.
- 7. Positive serologic findings for human immunodeficiency virus (HIV) antibodies, hepatitis B surface antigen (HBsAg) and /or hepatitis C virus (HCV) antibodies.

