# 8.4. Special Situations

# 8.4.1. Potential Cases of Drug-Induced Liver Injury

Humans exposed to a drug who show no sign of liver injury (as determined by elevations in transaminases) are termed "tolerators," while those who show transient liver injury, but adapt are termed "adaptors." In some subjects, transaminase elevations are a harbinger of a more serious potential outcome. These subjects fail to adapt and therefore are "susceptible" to progressive and serious liver injury, commonly referred to as drug-induced liver injury (DILI). Subjects who experience a transaminase elevation above 3 times the upper limit of

normal (× ULN) should be monitored more frequently to determine if they are an "adaptor" or are "susceptible."

In the majority of DILI cases, elevations in aspartate aminotransferase (AST) and/or alanine aminotransferase (ALT) precede total bilirubin (TBili) elevations (>2 × ULN) by several days or weeks. The increase in TBili typically occurs while AST/ALT is/are still elevated above  $3 \times ULN$  (ie, AST/ALT and TBili values will be elevated within the same lab sample). In rare instances, by the time TBili elevations are detected, AST/ALT values might have decreased. This occurrence is still regarded as a potential DILI. Therefore, abnormal elevations in either AST OR ALT in addition to TBili that meet the criteria outlined below are considered potential DILI (assessed per Hy's law criteria) cases and should always be considered important medical events, even before all other possible causes of liver injury have been excluded.

The threshold of laboratory abnormalities for a potential DILI case depends on the subject's individual baseline values and underlying conditions. Subjects who present with the following laboratory abnormalities should be evaluated further as potential DILI (Hy's law) cases to definitively determine the etiology of the abnormal laboratory values:

- Subjects with AST/ALT and TBili baseline values within the normal range who subsequently present with AST OR ALT values >3 × ULN AND a TBili value >2 × ULN with no evidence of hemolysis and an alkaline phosphatase value <2 × ULN or not available.
- For subjects with baseline AST **OR** ALT **OR** TBili values above the ULN, the following threshold values are used in the definition mentioned above, as needed, depending on which values are above the ULN at baseline:

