8.3.6. Vital Signs Data

The baseline measurement is the last pre-dose measurement.

These data will be listed and out of range values will be summarized in accordance with the sponsor reporting standards.

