8.3.7. ECG Data

The baseline measurement is the pre-dose measurement.

These data will be listed and out of range values will be summarized in accordance with the sponsor reporting standards.

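### SAP 8.3.5 sets no laboratory baseline and names only an out-of-range summary, so the group tables mix abnormalities present at entry with new ones

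*SAP*

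**What the plan says.** On laboratory data the SAP has one sentence, in 8.3.5: "Laboratory data will be listed and out of range values will be summarized in accordance with the sponsor reporting standards". The sponsor standards it refers to are in neither document.

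The two sections that follow use the same out-of-range wording but first set a baseline. For vital signs (8.3.6): "The baseline measurement is the last pre-dose measurement". For ECG (8.3.7): "The baseline measurement is the pre-dose measurement".

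SAP 8.3 fixes the layout: "A set of summary tables split by hepatic function group will be produced". Protocol section 2 makes safety a primary objective, "To evaluate the safety and tolerability of a single 840 mg IV dose of rivipansel in subject with moderate hepatic impairment", and in healthy controls, with safety laboratory tests among the named assessments.

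Entry rules differ between the groups on the tests to be tabulated:

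- Impaired group, Protocol 3.1: "Subjects should satisfy the criteria for Child-Pugh classification as Moderate Hepatic Impairment (Class B Score 7-9) for both assessments". Bilirubin, albumin and prothrombin time are three of the five scored items. Protocol 4.2.3 allows transaminases up to 5 × ULN (higher case by case) and other laboratory abnormalities influenced by the liver disease.
- Healthy group, Protocol 4.2.2: AST or ALT above ULN at screening excludes, and so does "Total bilirubin level > ULN".

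Scheduled safety samples fall at screening, Day 0 and Day 5. Under Protocol 9.3, screening laboratory results used for eligibility are source data that need not be reported. Day 0 is therefore the only routinely reported pre-dose value.

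**The concern.** The two groups are selected partly on the variables that the table will display. A between-group contrast in out-of-range values then partly restates the eligibility criteria. It is also least sensitive in the group the study was set up to examine, because a result already outside the range on Day 0 stays outside it when it gets worse.

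Liver tests are a natural place to look for a drug effect here. Protocol 1.2 reports one discontinuation for raised ALT after rivipansel in the thorough QT study. Protocol 8.4.1 recognises that a fixed limit is not enough when starting values differ: "The threshold of laboratory abnormalities for a potential DILI case depends on" each subject's own starting values and background disease. That rule detects individual cases and sets no standard for group tables, but the reason behind it applies to the summary as well.

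**Working it through.** The plan states no figure on this point, so there is none to reproduce. The group sizes agree with the total: 8 + 8 = 16.

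**1. How far Child-Pugh entry builds in abnormal results.** Inputs: the score table and Class B range of 7–9 (Protocol 3.1), and the exclusion of encephalopathy above Grade II (Protocol 4.2.3), which caps that item at 2 points. The other four items take 1–3 points.

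- All combinations: 2 × 3⁴ = 162. Totals of 7, 8 and 9 arise in 14 + 26 + 35 = 75 of them.
- None of bilirubin, albumin or prothrombin time above 1 point: 3 patterns (two with total 7, one with total 8), which reach Class B on ascites and encephalopathy alone.
- At least one of the three above 1 point: 75 − 3 = 72, or 72/75 = 96%.
- One named test of the three above 1 point: 40/75 = 53%, the same for each by symmetry.

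These are score patterns with equal weight, not patients. Reading them as out-of-range results assumes that the Child-Pugh cut-points lie outside the laboratory reference range. AST and ALT are not Child-Pugh items, so the count says nothing about them.

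**2. The group table with and without a drug effect.** Let p be the share of the 8 impaired subjects out of range on Day 0 for a given test. The documents give no value, so 25–100% is an assumption, with p = 0 added for reference. Values are taken as stable apart from any drug effect.

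- No effect: expected count on Day 5 = 8p.
- Chance of 4 or more of 8 with no effect: the sum over k = 4 to 8 of C(8,k) pᵏ(1−p)⁸⁻ᵏ.
- Illustrative effect that moves half of the subjects with normal values out of range: expected new cases = 8(1 − p) × 0.5.
- Total shown in the table with that effect = 8p + 8(1 − p) × 0.5.

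| p | Count, no effect | Chance of ≥4 of 8, no effect | New cases with effect | Total with effect |
|---|---|---|---|---|
| 0% | 0 | 0 | 4 | 4 |
| 25% | 2 | 0.11 | 3 | 5 |
| 50% | 4 | 0.64 | 2 | 6 |
| 75% | 6 | 0.97 | 1 | 7 |
| 100% | 8 | 1.00 | 0 | 8 |

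An expected count of 6 of 8 arises from p = 75% with no drug effect and equally from p = 50% with a substantial one. Without Day 0 in the table the two cannot be told apart. The healthy group starts from none above ULN at screening for AST, ALT and bilirubin.

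**3. Worsening in a subject already out of range.** Suppose that ALT doubles. For a subject raised at baseline, the ALT part of the Protocol 8.4.1 rule is the smaller of 8 × ULN and the greater of 2 × baseline and 3 × ULN.

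| Day 0 (× ULN) | Day 5 (× ULN) | Out of range, Day 0 / Day 5 | ALT threshold (× ULN) | Above threshold |
|---|---|---|---|---|
| 1.2 | 2.4 | yes / yes | 3 | no |
| 2.0 | 4.0 | yes / yes | 4 | no (equal) |
| 3.0 | 6.0 | yes / yes | 6 | no (equal) |
| 4.5 | 9.0 | yes / yes | 8 | yes |

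The out-of-range flag does not move in any row. The case rule responds in one row, and it also requires a bilirubin rise.

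**4. The same data against Day 0.** With stable values and no drug effect, the expected number of new abnormalities is 0 in both groups, whatever p is. The rise from 2 to 4 × ULN appears as a ratio to baseline of 2.0.

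**The case against.** The strongest reply is that little is lost. The sentence in 8.3.5 promises a listing first, and a doubled bilirubin can be read from about 16 subjects with two scheduled reported samples each. Protocol 9.3 provides for ongoing review and for a description of abnormalities of potential concern. Protocol 8.2.2 turns abnormal results into adverse events when they bring symptoms, further testing or treatment, or when the investigator or sponsor judges them so, and adverse events are reported by group. Protocol 8.4.1 catches potential DILI against baseline. All of this stands. A reader might infer that a drug effect on the liver tests could not be seen at all, and the documents do not support that.

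The second reply is that the unseen sponsor standards may already use a baseline. The SAP does not define out of range, and it uses the same words for vital signs and ECG directly after a baseline definition. The documents neither show nor exclude a baseline split. This limits the point to the text as written. It does not explain why laboratory data alone lack the definition.

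The third is that the built-in imbalance is easily exaggerated. A reader might infer a table of 8/8 against 0/8 with no drug effect. That would need p = 100% for the test in question, or all tests pooled into one row, which the SAP does not state. For the healthy group, a numeric ULN limit exists only for AST, ALT and bilirubin, and it applies at screening. The eligibility criteria permit raised transaminases in impaired subjects but do not require them, so a new elevation from a normal Day 0 value would still register.

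Finally, this is an estimation study with no hypotheses or decision rules and one scheduled post-dose laboratory sample. A shift table would therefore change no formal decision. That limits the weight of the point, but a primary safety objective still deserves a summary that can be interpreted.

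**Conclusion.** The point holds for the summary table and no further. SAP 8.3.5 defines no laboratory baseline and names only an out-of-range summary. Read as written, the by-group tables combine pre-existing with new abnormalities and do not show further worsening in impaired subjects who are already out of range on Day 0.

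Its size depends on an unknown, the share of impaired subjects out of range on Day 0. Under the assumed 25–100%, disease alone yields an expected 2 to 8 of 8 for a given test, against a healthy group screened to be within the ULN for AST, ALT and bilirubin. This assumes stable values from Day 0 to Day 5 and no baseline split in the sponsor standards. If the standards already contain one, what remains is a missing statement in the SAP. It is a worthwhile correction to a descriptive analysis and casts no doubt on the PK comparison.

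**What to change.** In SAP 8.3.5:

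1. Define the last pre-dose (Day 0) value as the laboratory baseline.
2. By hepatic function group, present the change and a shift table from Day 0 to Day 5, at least for AST, ALT, total bilirubin, alkaline phosphatase, albumin and PT/INR.
3. Identify post-dose abnormalities that are new or worsened relative to Day 0, and state what counts as worsened. A shift table with only low, normal and high categories would still show a rise from 2 to 4 × ULN as high to high. The change, or bands in multiples of the ULN, must carry that information.
4. Keep the listing and the out-of-range summary.
5. If the sponsor standards already do this, say so in the section.

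The Day 0 and Day 5 samples are already scheduled, so no extra blood, data or protocol amendment is needed. The cost is a paragraph of SAP text and slightly more programming. With 8 subjects per group and one scheduled post-dose sample, the analysis stays descriptive.
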